5.7. HANDLING OF PARTIAL DATES FOR MEDICATIONS

When determining prior or concomitant medications, partial start dates of prior and concomitant medications will be assumed to be the earliest possible date consistent with the partial date.

- Medication start dates with a missing day and non-missing month will be assumed to have occurred on the first day of the non-missing month, except for medications occurring in the first month of dosing, in which case the date will be one day before the first day of dosing.
- Medication start dates with missing day and month will be assumed to have occurred on the first day of the non-missing year (i.e., 1 January), except for medications occurring in the first year of dosing, in which case the date will be the informed consent date.
- Medications that are not ongoing and have a medication stop date with a missing day and non-missing month will be assumed to have stopped on the last day of the non-missing month.
- Medications that are not ongoing and have a medication stop date with a missing month will be assumed to have stopped on the last day of the non-missing year (i.e., 31 December).

5.8. HANDLING OF PARTIAL DATES FOR PROCEDURES

For records with a missing procedure date, the following procedure will be employed to determine whether the procedure is prior or concomitant:

- For a procedure with a missing or partially missing date performed on a scheduled visit, the date of the scheduled visit will be used.
- If a procedure was not scheduled, the missing part of the date will be imputed as discussed in [Section 5.9](#).

5.9. HANDLING OF PARTIAL DATES FOR OTHER DATA

Other data (such as disease history) with partial dates will be listed as collected. For calculation of time intervals, the dates will be imputed with the first day of the month (if the day is missing) or with 1 January (if both day and month are missing).

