#### **6.3.4.2. Survival Follow-up (Phase 2 only)**

There is no survival follow-up for Phase 1.

For subjects in Phase 2, after the first Treatment Follow-up Visit, subjects with progressive disease and/or who start new line of therapy will move into Survival Follow-up. Subjects should be contacted by telephone to assess for survival status every 2 months for up to 12 months after their last dose of study drug.

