7.7. EFFICACY ANALYSIS

7.7.1. Best Overall Response and Objective Response per RECIST 1.1

Best overall response (BOR) will be derived from time-point RECIST 1.1 assessments, either by IERC or by investigator. For the primary endpoint, tumor responses will be evaluated using IERC assessments. In the primary analysis, BOR will be evaluated over all on-study time-point assessments recorded before start of a new anti-cancer therapy, in consideration of RECIST 1.1 definition: “The best overall response is the best response recorded from the start of the study treatment until the end of treatment taking into account any requirement for confirmation. On occasion a response may not be documented until after the end of therapy so protocols should be clear if post-treatment assessments are to be considered in determination of best overall response” (Eisenhauer *et al 2009*). Since all assessments are considered for BOR, the confirmed objective response or stable disease (SD) may occur after a transient time-point progressive disease (PD) assessment(s).

In the secondary analysis, conducted for sensitivity evaluation, an alternative, more conservative approach will be used, evaluating BOR only over time-point assessments until first observed PD, as initially proposed in RECIST 1.0 (Therasse *et al 2000*). Such a definition was implemented in the Charter of IERC, therefore BOR evaluation derived by IERC will be used as sensitivity analysis.

Confirmation of objective response (complete response [CR] or partial response [PR]) is required for respective BOR of CR or PR. Confirmation must be obtained at a subsequent assessment at least 4 weeks apart. In case of CR, the confirmatory assessment must be performed at a consecutive assessment, except for intercurrent non-evaluable assessments.

In case of PR, confirmatory assessment after initial CR/PR may be obtained a) in the primary analysis any time at least 4 weeks apart from the initial assessment, without restrictions on intercurrent assessment b) in the IERC-derived BOR evaluation, any time after 4 weeks and after at most 1 intercurrent assessment of non-evaluable (NE) or SD.

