7.7.3. Duration of Response

Duration of response (DOR) will be analyzed only for subjects who responded to the study treatment. DOR is defined as the time from first observation of CR or PR which was subsequently confirmed until the first time of disease progression or death by any cause within 12 weeks of last tumor assessment. All assessments performed before initiation of a new anti-cancer therapy will be considered for evaluation of DOR. Similar to evaluation of BOR, in the primary analysis any transient time-point PD(s) will be disregarded for determination of DOR when followed by confirmed objective response or durable stable disease, as defined in section 7.1.1. In the alternative (sensitivity) analysis, DOR will be counted using the date of first observed PD, whether transient or not.

The starting event for DOR will be the date of first objective response. The terminating event will be date of PD or death within 12 weeks of last tumor assessment, whichever occurs first. The censoring event will be the earliest of the dates of last evaluable assessment, last evaluable assessment performed before initiation of new anti-cancer therapy (if applicable), or before 2 or more missed imaging assessments (i.e., no assessment within 90 days) followed by PD or death.

DOE will be reported in months and summarized by quartiles estimated from Kaplan-Meier curve, as well as Kaplan-Meier estimates at 6, 9, 12, 18 months. Number and percent of censored and non-censored observations and a plot Kaplan-Meier curve will be provided.

In addition, duration of observation of DOE (whether censored or not) will be summarized as “Observed DOE”, including the shortest and longest observation will be provided with censoring indicator.

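### SAP 5.9 moves partial dates to the first of the month or 1 January with no lower bound, so a partial death date can fall before the subject was last known alive, and a partial new-therapy date can remove a progression from DOR

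*SAP*

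**What the plan says.** SAP 5.6, 5.7 and 5.8 set partial-date rules for adverse events, medications and procedures. SAP 5.9 covers what is left: "Other data (such as disease history) with partial dates will be listed as collected". It continues: "For calculation of time intervals, the dates will be imputed with the first day of the month (if the day is missing". When the month is missing as well, the date becomes 1 January. The adverse-event rule in 5.6 bounds onset by first dose and resolution by study discontinuation, death or last dose plus 90 days. SAP 5.9 has no such bound.

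SAP 5.7 also moves dates early: "When determining prior or concomitant medications, partial start dates of prior and concomitant medications will be assumed to be the earliest possible date". Its stated purpose is to classify medications as prior or concomitant.

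The dates at issue enter the efficacy analysis as follows:
- **OS (SAP 7.7.10)** runs from first dose to death. Last contact is used only to censor subjects who have not died.
- **DOR (SAP 7.7.3):** "All assessments performed before initiation of a new anti-cancer therapy will be considered for evaluation of DOR". A responder who starts new therapy without a counted event is censored at the last evaluable scan before it.
- **BOR (SAP 7.7.1):** "BOR will be evaluated over all on-study time-point assessments recorded before start of a new anti-cancer therapy".
- **PFS (SAP 7.7.9, primary analysis)** applies its censoring, including censoring at new therapy, only to patients without a non-transient progression or death.

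Once a Phase 2 subject is in survival follow-up, Protocol 6.3.4.2 says: "Subjects should be contacted by telephone to assess for survival status every 2 months".

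**The concern.** Dates of death and of the next therapy are often learned after the event, by telephone or from another treating centre, so a missing day is plausible. Setting such a date to the earliest possible day is not neutral. For a death it can contradict a recorded contact and shorten OS. For a new-therapy start it can reverse the true order of progression and switch, because progression is what usually prompts the switch and the two may fall in the same month. In DOR that would turn an event into censoring in the very subjects who progressed, so the censoring would be informative. DOR matters here: SAP 4.2 times the filing analysis to give 6 months of follow-up on confirmed responses.

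**Working it through.** The plan gives no figure for the effect of this rule, so there is none to reproduce. The check applies the rule to each of the 366 days of 2020, taken as equally likely. Gaps between dates are assumptions. Intervals follow SAP 7.2: (end − start + 1) days, divided by 30.4375 for months.

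**1. Size of the shift.** Day missing: the sum over months of L(L−1)/2, for month length L, is 7×465 + 4×435 + 406 = 5,401; 5,401/366 = 14.8 days early on average, at most 30. Day and month missing: 365/2 = 182.5 days on average, at most 365.

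**2. Imputed death before last contact, day missing.** With contact g days before death, this needs a day of the month greater than g + 1. The share of days is (366 − 12(g+1))/366 for g up to 28.
- g = 7: 270/366 = 74%
- g = 14: 186/366 = 51%
- g = 21: 102/366 = 28%
- g = 30 or more: 0%, because the contact then never falls after the first of the month of death

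With g assumed uniform over 0 to 61 days, roughly the interval between calls, the share is 24%. For year-only dates it is 91%.

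**3. OS example.** First dose 4 Nov 2019, last contact 20 Oct 2020, death 27 Oct 2020.
- True OS: 359/30.4375 = 11.79 months.
- Follow-up to last contact: 352/30.4375 = 11.56 months.
- Death recorded as Oct 2020, imputed to 1 Oct: 333/30.4375 = 10.94 months, shorter than the time the subject was known to be alive.
- Death recorded as 2020, imputed to 1 Jan: 59/30.4375 = 1.94 months.
- With first dose on 10 Mar 2020 instead and death recorded as 2020: −68/30.4375 = −2.23 months, before first dose.

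**4. Death as an event in DOR and PFS.** SAP 7.7.3 counts a death within 12 weeks (84 days) of the last tumor assessment. Take a scan on 10 Jan 2021 and a death on 20 Apr, 100 days later, recorded only as April. Imputed to 1 Apr, it is 81 days after the scan, so a non-event becomes an event. In PFS, a death that is the event is moved earlier by the shift in step 1.

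**5. Progression scan on or after the imputed therapy start, day missing.** With therapy g days after the scan, the two share a month on (366 − 12g)/366 of days, for g up to 28.
- g = 7: 282/366 = 77%
- g = 14: 198/366 = 54%
- g = 21: 114/366 = 31%
- g = 28: 30/366 = 8%

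For year-only dates, imputed to 1 January, the share is 92% to 98% over the same gaps.

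**6. DOR example.** Scans every 6 weeks, response first seen 16 Dec 2019, progression scan 13 Jul 2020, new therapy 24 Jul recorded as Jul 2020 and imputed to 1 Jul. The 13 Jul scan now follows the therapy start. The event at 211/30.4375 = 6.93 months becomes censoring at the 1 Jun scan, 169/30.4375 = 5.55 months.

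**The case against.** The strongest case against has four parts.

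**Scope.** SAP 5.9 names neither date, and its only example is disease history. It imputes for time intervals, and 5.7 for classifying medications. In DOR the therapy date is not an interval endpoint; it decides which scans count. This stands in part. For death the objection fails: OS is a time interval and no other rule exists. For therapy starts, using 5.9 or 5.7 for the scan cut-off is the natural reading but not an explicit one.

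**Data collection.** Protocol 6.4.1.9.1 requires the Safety Follow-up Visit before any new therapy that starts within 4 weeks of the last dose. Deaths reported as SAEs reach the sponsor within 24 hours (Protocol 7.2.2.1). Two-monthly calls usually bracket a death well within a year. This makes year-only death dates unlikely and partial dates perhaps uncommon, but it does not exclude a missing day.

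**Size.** A reader might infer that each partial therapy date has about an even chance of deleting the progression, and that median DOR rises by about 12%. The even chance is only the 14-day case of a range from 77% to 8%. The 12% assumes 10 switching responders, 20% partial dates and a 14-day gap: 10 × 0.2 × 0.54 = 1.08 events lost, and 10/8.92 = 1.12. It also ignores the follow-up that is lost. With the example's 6.93 and 5.55 months, (69.3 − 1.08 × 1.38)/8.92 = 7.60, a rise of about 10%. Neither the 10 nor the 20% is in the documents, and the SAP uses Kaplan-Meier quartiles, not an exponential median. A reader might also infer a material effect on ORR through SAP 7.7.1. That needs a switch of therapy in the same month as a confirmatory response scan, and nothing in the documents shows how often this would happen.

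**Importance.** OS and DOR are secondary endpoints in a single-arm study without formal hypothesis testing (SAP 7.1), an early death date does not flatter the drug, and partial dates are listed as recorded. All true. It limits the consequence but does not make an impossible survival time acceptable.

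**Conclusion.** The point holds for both dates, more firmly for death.

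**Death.** A stated rule, followed literally, can give a death before a date known alive or, for a year-only date, before first dose. With the day missing, the shift averages about 15 days, and the contradiction arises only when last contact fell in the same month. The error shortens OS and can move death events in PFS and DOR.

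**Subsequent therapy.** On the natural reading, a progression scan in the same month as the switch can be dropped and the responder censored at the previous scan, which can lengthen estimated DOR. The 77% to 8% range depends on assumed gaps and applies only to records with the day missing. Primary PFS is little exposed to this date.

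The two errors act in opposite directions on different endpoints. The documents do not give the rate of partial dates, so no net effect on median OS or DOR can be stated.

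**What to change.** In SAP 5.9, exempt the death date and the start of subsequent anti-cancer therapy from the first-of-month and 1 January rule, and add:
- **Death.** Impute within the known month or year, no earlier than the day after the last date known alive and no later than data cutoff. The SAP should name the point used within that range; mid-month is one option, not a requirement. If no date satisfies the bounds, query the record.
- **Subsequent therapy.** Impute within the known month or year, no earlier than the day after the last study-drug dose. Protocol 5.5.2 already bars other anticancer drug treatment during the treatment period.
- **DOR.** When only the day of the therapy start is missing, count a progression scan in that same month as preceding the therapy. This is the conservative choice. Do not extend it to year-only dates, where it could admit scans taken on another therapy.
- **Sensitivity analysis.** Repeat with the earliest possible therapy date.
- **Listings.** Flag imputed dates.

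The cost is a few SAP sentences and minor extra programming before the filing analysis. DOR may come out slightly less favourable.

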5.10. HANDLING OF MISSING DATA

Missing data will not be imputed, except for:

- Missing date parts, i.e., partial dates, discussed above
- Missing AEs grade severity and relationship to study drug of AEs, discussed in [Section 7.6.2](#)
- Missing efficacy assessments discussed in Section 7.7.

6. ANALYSIS SETS

The following analysis sets will be used for analysis of Phase 2 data:

Table 2: Definitions of Analysis Sets

Analysis Set	Definition	Analysis to Be Conducted	Interim Analysis
All subjects analysis set	Includes all subjects who signed informed consent form (ICF), irrespective if they passed or failed screening for Inclusion and Exclusion criteria.	Will be used only for listing of all subjects who signed informed consent who either received study treatment or were excluded from the study during the screening period due to failure to meet eligibility criteria.	All patients who signed informed consent by the cut-off date for data.
Safety (Note: All dosed subjects)			
Safety analysis set (SAS)	Includes all subjects who received ≥ 1 dose of study treatment.	It will be used for safety evaluation, as the primary analysis in the final analysis of data and as a secondary set in any interim analysis.	All patients dosed by the cut-off date for data.
ITT (Note: No exclusions based on information obtained after study treatment initiation)			
ITT efficacy analysis set (ITT EAS)	Includes all subjects who received ≥ 1 dose of study treatment, with measurable disease at baseline (per IERC).	Primary analysis set for efficacy.	All patients with measurable disease at baseline (per IERC) dosed by the cutoff-date for enrollment.

ITT Prior Line of Therapy analysis set (ITT PLT)	Includes all subjects who received ≥ 1 dose of study treatment, with measurable disease at baseline (per IERC), and had prior line of platinum-based treatment in metastatic, persistent or recurrent setting, as determined by Independent Review Committee	Secondary analysis set for efficacy	N/A
Per Protocol (Note: Possible exclusions based on information obtained after study treatment initiation)			
Per Protocol (PP) Efficacy Analysis Set (PP EAS)	Includes all subjects who received ≥ 1 dose of study treatment, had measurable disease at baseline by IERC, and were not excluded due to important protocol deviations.	The PP EAS set will be used for sensitivity analysis of the primary efficacy analysis.	All patients dosed by the cutoff-date for enrollment, had measurable disease at baseline by IERC, and were not excluded due to important protocol deviations (exclusions will be decided case by case).
Pharmacokinetic analysis set (PK analysis set)	Includes all subjects who have completed ≥ 1 infusion of study drug, and who have sufficient evaluable drug concentration measurements prior to and after treatment.	Pharmacokinetics Analysis Set will be used for pharmacokinetic analysis that will be conducted according to a separate pharmacokinetic analysis plan.	

6.1. ANALYSIS TO BE CONDUCTED FOR DIFFERENT ANALYSIS SETS

Table 3 below shows analysis sets used for different data omitting All Subjects Analysis Set (as this is only used for listing of screened and enrolled subjects) and PK Analysis Set (as this analysis will be conducted according to a separate PK analysis plan).

Table 3: Applications of Analysis Sets

Analysis	ITT EAS	ITT PLT	PP EAS	SAS
Subject Disposition	2	2		1

Protocol Deviations				1
Demographic and Baseline Characteristics	2	2		1
Medical History				1
Ongoing Medical History				1
Cancer History	1	1		2
Prior Cancer Therapies and Procedures	1	1		
Prior and Concomitant Medications				1
Drug Exposure				1
Adverse Events				1
Anti-Drug Antibodies				1
Clinical Laboratory Tests				1
Body Weight and Vital Signs				1
12-lead ECG				1
Pregnancy tests				1
ORR per RECIST 1.1	1	1	2	
Time to Response	1	1	2	
Duration of Response	1	1	2	
Disease Control Rate	1	1	2	
Tumor Control Rate	1	1	2	
Progression-Free Survival	1	1	2	
Overall Survival	2	2		1

Legend: 1 = Primary Analysis, 2 = Secondary Analysis

6.2. PROTOCOL DEVIATIONS AND EXCLUSIONS FROM ANALYSIS SETS

A protocol deviation is any change, divergence, or departure from the study design or procedures defined in the protocol. Important protocol deviations are a subset of protocol deviations that may significantly impact the completeness, accuracy, and/or reliability of the study data or that may significantly affect a subject's rights, safety, or well-being ([ICH E3 Questions and Answers R1](#)).

Protocol deviations will be reviewed by study team to designate important protocol deviations. These important protocol deviations will be summarized by category, and all protocol deviations will be listed.

Important protocol deviations may lead to exclusions from Per Protocol analysis sets such as PP EAS. The exclusions will be finalized before clinical database is available for analysis.

7. STATISTICAL CONSIDERATIONS

All analyses described in this plan are considered a priori analyses as they have been defined prior to database availability for analysis. The COVID-19 pandemic may impact Agenus ability to complete data monitoring, collection, and cleaning to achieve the data lock as originally planned for our clinical programs. As a result, a priori analysis of Agenus clinical trial data may be completed prior to all data locked; however, all analysis will occur using locked and frozen clinical database records and ensuring trial data integrity is maintained as locked or frozen on the subject and visit levels. Clinical data management will notify the team when data are available (all locked or frozen) for download and the planned analysis. The impact of lack of source data verification or principal investigator (PI) signature will be performed at the time of data download. Only significant impact/risks to analysis of data, with the planned mitigation, will be discussed in the clinical study report (CSR). Clinical data management will keep a log of requested data changes after the data download for the analysis, result of completion of Source Data Verification (SDV) or new information provided. Requested changes will be reviewed by the team before changes are made to the database. An additional analysis may be performed if data changes would affect study conclusions; additional analysis will be described in the applicable SAP. All other analyses, if any, designed after completing analysis specified in this SAP and additional analysis plans referred by the SAP, will be considered post-hoc analyses and will be described in a separate exploratory analysis plan (if applicable).

All summaries and statistical analysis will be performed using SAS Software (SAS Institute Inc., Cary, NC, USA), version 9.4 or later, or R (R Foundation for Statistical Computing, Vienna, Austria), version 3.6.3 or later.

7.1. SAMPLE SIZE

No formal hypothesis testing is being planned for this Phase 2 study, rather the goal is to estimate the primary endpoint (ORR per IERC based on RECIST 1.1) with confidence intervals (CI), interpreted as a plausible range for a true (unobserved) ORR that could be interpreted considering historical data.

The sample size was planned to allow for exclusion of the ORR of 5% by the lower confidence limit Wilson score CI and to provide adequate safety data. With 150 subjects originally planned for the final analysis, the power to exclude an ORR of 5% by the lower limit of the 95% Wilson score interval is 92.2% and 96.2%, assuming a true ORR of 12% and 13%, respectively. The sample size for 150 subjects also provides $\geq 77\%$ probability to observe an AE with an underlying rate of $\geq 1\%$.

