### 8.1. Sample Size

The study includes 2 phases: Phase 1: Dose Escalation Phase, and Phase 2: Expansion Phase. The total sample size for both phases is expected to be approximately 200 subjects.

#### 8.1.1. Phase 1

It is expected that approximately 50 subjects will be enrolled in the Phase 1 part of the study. The sample size in the Phase 1 is not driven by statistical hypothesis testing, but driven by clinical considerations. Final sample size in this phase may vary depending on the total number of dose levels to be tested, and subject replacement for DLT evaluation, if applicable.

#### 8.1.2. Phase 2

The aim in this phase is to detect preliminary evidence of clinical activity in subjects with metastatic cervical cancer. The primary endpoint is the ORR per IERC based on RECIST 1.1. ORR will be estimated as binomial proportion of best overall response (BOR) of confirmed PR

or CR and reported with 95% Wilson score confidence interval (CI); the CI will be interpreted as a plausible range for a true (unobserved) ORR.

Phase 2 is expected to enroll approximately 150 subjects. With 150 subjects in the final analysis, the power to exclude an ORR of 5% by the lower limit of the 95% Wilson score interval is 92.2% and 96.2%, assuming a true ORR of 12% and 13%, respectively. The sample size will provide  $\geq 77\%$  probability to observe an AE with an underlying rate of  $\geq 1\%$ . With 100 patients in the interim analysis, the power to exclude an ORR of 5% by the lower limit of the two-sided 95% Wilson score interval will be 77.4% and 85.2%, assuming a true ORR of 12% and 13%, respectively.

Historical published data may be used for the interpretation of the clinical significance of the study endpoints.

Interim analyses will be performed to assess the safety and efficacy (using the ORR and selected secondary efficacy endpoints) when (1) data are available for approximately 30 subjects treated for at least 3 months and (2) approximately 3 months after approximately 100 patients are dosed. No early stopping for efficacy will be performed, as a more complete safety assessment and evaluation of durability of responses is necessary for determination of risks and benefits. Consequently, interim analyses will not affect the overall type I error. A non-binding futility analysis may be performed using methods described in the statistical analysis plan. Additional interim analyses for safety and efficacy assessment may be performed.

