## **8.3. Description of Statistical Analyses**

### **8.3.1. General Considerations**

All data recorded during the study will be presented in individual data listings performed on the safety analysis set. All data will be evaluated as observed, and no imputation method for missing values will be used unless otherwise specified. All data will be presented in a descriptive manner. Statistical inference of the primary efficacy endpoint will be performed for the efficacy expansion cohort based on the pre-planned significance level.

Descriptive statistics will be used in general to summarize trial results, i.e., statistics for continuous variables may include means, standard deviations, medians, and ranges (min, max). Categorical variables will be summarized by counts and percentages. Unless otherwise specified, calculation of proportions will be based on the number of subjects in the analysis set of interest. Counts of missing observations will be included in the denominator and presented as a separate category if not otherwise specified in the SAP.

The DLT analysis set is the underlying dataset for determination of the safety. Safety analyses will be performed on the Safety analysis set. Analyses of PK variables will be performed on the PK analysis set. The primary analysis of the ORR and other efficacy variables will be based on the evaluable efficacy analysis set, defined as all subjects dosed with study drug who had measurable disease at baseline by IERC assessment. Details of the analysis will be described in the SAP.

Unless otherwise specified, endpoint analyses will be performed separately for Phase 1 and Phase 2.

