#### **8.3.2.2. In Phase 2: Objective Response Rate**

- The primary endpoint for Phase 2 is the confirmed ORR according to RECIST 1.1, as determined by an IERC. ORR will be estimated as the binomial proportion of patients with BOR of PR or CR, taking into account the following requirement for confirmation: for PR or CR, confirmation of the response according to RECIST 1.1 will be required at no sooner than 4 weeks after initial documentation of CR or PR. ORR will be reported with two-sided, 95% Wilson score CI.

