4.2. INTERIM ANALYSES AND DATA MONITORING

The Protocol specified that Phase 2 is designed to have at least 2 interim analyses of the primary endpoint and selected secondary efficacy and safety endpoints. No early stopping for efficacy will be performed, as a more complete assessment of safety and durability of responses will be required for evaluation of risks and benefits. Consequently, the overall type I error will not be affected by the interim analyses.

The first pre-specified interim analysis was performed based on the prospectively defined interim analysis SAP, when data were available for approximately 30 subjects treated for at least 3 months. The analysis included, for efficacy, all subjects dosed as of 15 Jul 2019 (N = 44), including N = 42 consecutive subjects with measurable disease at baseline for the primary analysis of efficacy. For safety, interim analysis included all subjects dosed by 16 Oct 2019 (the date of the data cutoff), N = 60 such subjects available at the time of the original analysis (however, it was discovered later during re-analysis of the same cohort, using data cutoff of 27 Mar 2020, that N=61 subjects had been actually dosed by 16 Oct 2019; one subject was not accounted for in the original safety analysis due to delayed data entry; the missing subject was included later in an updated analysis). The analysis was conducted according to a standalone Interim Analysis SAP. A non-binding futility assessment consisted of evaluation of conditional and predicted probability (He *et al 2012*) of excluding the ORR of 5% by the lower limit of the Wilson's confidence interval for observed ORR, if the study continued enrollment to 100 and 150 patients.

The second pre-specified analysis was originally planned 3 months after approximately 100 subjects have been dosed and was to include, as the primary analysis of safety and efficacy, all subjects in the evaluable efficacy analysis set among the first approximately 100 subjects dosed. The goal of this analysis was to support regulatory BLA filing. However, due to fast accrual at the final stage of enrollment (consequently short follow-up at the time of the planned analysis) and in consideration of feedback received from FDA, the plans for this analysis were modified: the analysis was replaced by BLA Filing analysis below described below.

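### Does the unnumbered significance level in Protocol 8.3.1 conflict with the SAP's plan for no formal test of the primary response rate?

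*SAP*

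**What the plan says.** Protocol 8.3.1, General Considerations, first says that all data are to be presented descriptively and then adds: "Statistical inference of the primary efficacy endpoint will be performed for the efficacy expansion cohort based on the pre-planned significance level". No value for that level appears in either document.

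SAP 7.1 takes the estimation view: "No formal hypothesis testing is being planned for this Phase 2 study, rather the goal is to estimate the primary endpoint". Protocol 8.1.2 reads the interval the same way: "the CI will be interpreted as a plausible range for a true (unobserved) ORR". It also allows historical published data to inform interpretation.

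The interval is fully specified. Protocol 8.3.2.2: "ORR will be reported with two-sided, 95% Wilson score CI". SAP 7.2 repeats the two-sided 95% Wilson interval and says that no multiplicity adjustment is made.

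The 5% reference rate enters through the sample size, in Protocol 8.1.2: "With 150 subjects in the final analysis, the power to exclude an ORR of 5% by the lower limit of the 95% Wilson score interval". The figures given there are 92.2% at a true ORR of 12% and 96.2% at 13%. SAP 7.1 repeats these figures. Under SAP 4.2 the same criterion served the non-binding futility assessment at the first interim analysis.

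On the interim analyses, SAP 4.2 states: "Consequently, the overall type I error will not be affected by the interim analyses". Protocol 8.1.2 and 8.3.5 say the same, and the reason given each time is that there is no early stopping for efficacy.

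**The concern.** A significance level and a type I error belong to a test. SAP 7.1 says there is none, yet the requirement that the Wilson lower limit exceed 5% sized the trial and informed the futility assessment. SAP 4.1 lists the SAP's departures from the protocol and does not mention this one. The analysis is meant to support a licence application, so it would matter if readers could not tell a prespecified success criterion from a descriptive reference.

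A second point adds to the unease. Neither document gives the number of responders needed or the exact error of the rule at a true ORR of 5%. A reader who infers one-sided 2.5% from a two-sided 95% interval would be somewhat optimistic, because the Wilson interval is approximate. The size of the primary efficacy set is also not fixed. Enrolment is about 150, and the set is restricted to dosed subjects with measurable disease by independent review. At the first interim analysis 44 subjects had been dosed, "including N = 42 consecutive subjects with measurable disease at baseline for the primary analysis of efficacy".

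**Working it through.** **1. Reproduce the stated power.** Inputs from Protocol 8.1.2 and SAP 7.1: n = 150, reference rate 5%, two-sided 95% Wilson interval (z = 1.96), true ORR 12% or 13%.

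Wilson lower limit for x responders, with p = x/n:

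L = [p + z²/(2n) − z·√(p(1−p)/n + z²/(4n²))] / (1 + z²/n)

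With n = 150: z²/(2n) = 0.01281, z²/(4n²) = 0.0000427, 1 + z²/n = 1.02561.

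- x = 12, p = 0.0800: L = (0.0800 + 0.0128 − 0.0453)/1.0256 = 4.64%, which does not exclude 5%.
- x = 13, p = 0.0867: L = (0.0867 + 0.0128 − 0.0468)/1.0256 = 5.13%, which excludes 5%.

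The rule is therefore 13 or more responders. Exact binomial tails:

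- P(X ≥ 13 | 12%) = 92.19%, stated as 92.2%.
- P(X ≥ 13 | 13%) = 96.16%, stated as 96.2%.
- P(X ≥ 13 | 5%) = 3.85%, not stated.

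At n = 100 the rule is 10 or more, with power 77.43% and 85.23% (Protocol 8.1.2 states 77.4% and 85.2%) and an error of 2.82%. All four printed power figures are right.

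**2. Is the rule identifiable from what is printed?** Two alternatives at n = 150 fail to match:

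| Rule | Responders needed | Power at 12% / 13% |
|---|---|---|
| Two-sided 95% Wilson | 13 | 92.2% / 96.2% |
| One-sided 95% Wilson | 12 | 95.5% / 98.0% |
| Exact, one-sided 2.5% | 14 | 87.3% / 93.3% |

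Of the three, only the two-sided Wilson rule returns the stated figures. The threshold follows from the printed inputs.

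**3. Where could the choice of reading alter a conclusion?** At n = 150, Wilson and an exact 2.5% rule disagree only at x = 13. There the Wilson limit is 5.13%, the Clopper-Pearson limit is 4.70% and the exact one-sided p-value is 3.85%. At x = 14 the exact p-value is 1.87% and the two agree. P(X = 13) is 4.9% at an ORR of 12% and 2.9% at 13%.

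**4. Sensitivity to the size of the primary set.**

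| n | Basis | Threshold | Error at 5% | Power at 12% / 13% |
|---|---|---|---|---|
| 160 | Assumed over-enrolment | 14 | 3.05% | 92.2% / 96.3% |
| 150 | As planned | 13 | 3.85% | 92.2% / 96.2% |
| 148 | Two exclusions in all | 13 | 3.51% | 91.3% / 95.7% |
| 143 | 150 × 42/44 | 13 | 2.76% | 88.8% / 94.1% |
| 127 | 150 × (1 − 0.155) | 12 | 2.57% | 84.7% / 91.2% |

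The last row takes the upper 95% exact limit for 2/44, 15.5%, as the loss. That is pessimistic, since Protocol 4.2 (criterion 4) and 6.4.4.1 require central confirmation of measurable disease before the first dose. Over n = 127 to 160 the error moves in a sawtooth between 2.29% (n = 154) and 4.66% (n = 139), as expected for an approximate interval on a discrete outcome.

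**5. Set the texts side by side.** Protocol section 8 allows the SAP to modify the protocol's plans and asks for an amendment only for major changes to the primary endpoint's definition or analysis. On this point the estimator, interval and confidence level are identical in both documents. The type I error sentences claim only that interim looks add nothing, which is true when no look can stop the trial for efficacy.

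**The case for a change.** The strongest case for acting is that the contradiction is real on the page. A pre-planned level without a value cannot be checked, the SAP's list of changes is silent about it, and the 5% rule does criterion-like work without being called a criterion. In a filing analysis, a line settling its status would cost almost nothing, and a reader who assumes 2.5% would be told the actual 3.85%.

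Most of the facts in this stand. The protocol sentence is loosely worded, and SAP 4.1 could have mentioned it. The inference drawn from them does not stand. Interval estimation is itself statistical inference, and a two-sided 95% interval is a natural reading of the phrase in Protocol 8.3.1. No passage makes exclusion of 5% a condition for declaring success. SAP 7.1 answers the status question for anyone who reads it, and Protocol 8.1.2 agrees. The exact error would be an essential disclosure for a formal test. For a reference value read off a confidence interval it is background, and it can be recomputed from the printed inputs.

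**Conclusion.** No change to the plan is needed. An analyst following the documents as written computes the confirmed ORR with its two-sided 95% Wilson interval and reads it against 5% and historical data. The result is the same whether Protocol 8.3.1 is taken literally or as superseded by SAP 7.1. The printed power figures are correct, and the statement about interim analyses and type I error is sound given that there is no efficacy stopping.

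The size of the issue is small. The rule's exact error at a true ORR of 5% is 3.85% at n = 150 and stays between 2.29% and 4.66% for n from 127 to 160. At n = 150 the reading of the result would differ only at exactly 13 responders, and only against an exact one-sided 2.5% standard that neither document sets. A sentence in SAP 4.1 noting the wording would be tidy, but it would alter no analysis, sample size or conclusion.

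This rests on taking SAP 7.1 as the governing statement and on 5% not being used elsewhere as a formal success threshold. Nothing in the two documents suggests that it is.
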